1 ABBREVIATIONS USED IN THE PROTOCOL

Abbreviation	Term
AE	Adverse event
CHIP	Complete Health Improvement Program
EHR	Electronic Health Record
GAD-7	General Anxiety Disorder 7
GIRB	Geisinger IRB
HbA1c	Hemoglobin A1c
HIPAA	Health Insurance Portability and Accountability Act
IRB	Institutional Review Board
ITLC	Intensive Therapeutic Lifestyle Change
PHQ-9	Patient Health Questionnaire 9
PHI	Protected Health Information

2 ABSTRACT

Type 2 diabetes mellitus (T2DM) is a driver of poor health outcomes and high healthcare costs. Comprehensive lifestyle change can improve glycemic control, reduce complications, and reduce cost of care among patients with T2DM. Unfortunately, many patients fail to achieve adequate lifestyle change and thus experience adverse health events and/or become dependent upon expensive medical care. The Complete Health Improvement Program (CHIP) is an Intensive Therapeutic Lifestyle Change program administered in the outpatient setting. This is a pilot randomized-controlled trial comparing the clinical, utilization, and financial outcomes of adult health plan members with T2DM offered CHIP versus those only offered standard health plan coverage.

Sixty GHP members will be randomized 1:1 (stratified by most recent HbA1c value) into either the CHIP intervention group or the control group. The intervention group will attend 18 classes covering topics such as diet, sleep, exercise instruction, stress management, and toxic substance avoidance. Biometrics (weight, BMI, waist circumference, systolic/diastolic blood pressure), biomarkers (HbA1c, LDL-C) and psychometrics (Wellbeing360 survey) will be collected on all participants at baseline, 3-months and 6-months.

We hypothesize that GHP members with type 2 diabetes offered CHIP in addition to standard insurance coverage will have improvement in HbA1c and as well as in other biometrics, biomarkers, psychometrics and utilization/financial outcomes. The primary aim is to compare change in HbA1c, LDL-C, systolic blood pressure, body mass index, and waist circumference for GHP members offered CHIP versus members offered standard insurance coverage at 3- and 6-months. Since this is a pilot study, the focus of the analysis will be estimating the mean and standard deviation of the change at 3- and 6-month for each primary and secondary outcome. We will also estimate the difference of the changes between groups and the variability.

We seek to validate a scalable and replicable intervention which could be offered by a health plan alongside standard medical coverage to improve key health and financial outcomes for members with T2DM.

3 BACKGROUND AND SIGNIFICANCE

Type 2 diabetes mellitus (T2DM) is a key driver of poor health outcomes and high cost of healthcare in the United States. T2DM affects approximately 10% of adults in the United States and is associated with complications including cardiovascular events, loss of vision, diabetic kidney disease, and premature death (Center for Disease Control and Prevention, 2020). Healthcare costs are 2.3 times higher for patients with T2DM, and total direct costs of type 2 diabetes care exceed \$230 billion annually (American Diabetes Association, 2018).

Lifestyle intervention can dramatically influence the course of T2DM. For example, in the DiRECT trial, 46% of patients undergoing intensive calorie reduction (825-853 calories per day) followed by gradual dietary advancement achieved clinical remission of T2DM, defined as HbA1c below 6.5% while off all diabetes medications (Lean, Leslie, Barnes, & Brosnahan, 2018). Similarly, 30% of patients in a cohort drawn from the ADDITION-Cambridge trial achieved remission of T2DM through lifestyle change alone (Dambha-Miller, Day, Streitz, & Griffin, 2019). Unfortunately, in the real world most patients with T2DM fail to achieve clinical remission, and only about half of patients achieve an HbA1c below 7% even with medications (Edelman & Polonsky, 2017).

Several shortcomings of the most common lifestyle approaches in T2DM limit their population health impact. First, protocols based on dramatic calorie reduction may be challenging to sustain on a long-term basis. Admittedly, 24-month follow-up of the DiRECT trial cohort found 36% of intervention arm subjects remained in diabetes remission (Lean, Leslie, Barnes, & Brosnahan, 2018). However, follow-up of calorie restriction programs has been inconsistent beyond 24 months (Dombrowski et al. 2014). Second, achieving a consistent approach to lifestyle change in a real-world health system is challenging due to competing demands on providers and a lack of standardization. For example, 2019 guidelines from the American Diabetes Association (ADA) suggest that each patient develop a personalized diabetes self-management education and support (DSMES) plan, allowing some variety in lifestyle strategies (American Diabetes Association, 2019). Unfortunately, as evidenced by high rates of medication prescription and poor clinical outcomes, adequate DSMES plans are not consistently implemented. Lastly, interventions focused narrowly on parameters specific to diabetes, such as glycemic control and body mass

index, may not be optimized to achieve other important health outcomes such as cardiovascular prevention, dementia prevention, and cancer prevention.

An alternative approach to lifestyle intervention in T2DM would be to apply a lifestyle program designed to optimize overall health rather than one specifically targeting T2DM. In theory, such an approach could improve diabetes-related outcomes and might additionally help prevent adverse health events which are less directly linked to T2DM. Such an approach would offer the potential to achieve overall wellness and reduce overall healthcare costs. From the perspective of a healthcare payer, a standardized and scalable program offering general health benefits would be an appealing population health tool for improving members' health while also controlling healthcare costs.

Intensive Therapeutic Lifestyle Change (ITLC) describes comprehensive lifestyle programs aiming to improve outcomes for multiple common chronic conditions simultaneously. ITLC programs are designed to target the root causes common to the pathophysiology of multiple interrelated chronic conditions, including cardiovascular disease, cerebrovascular disease, fatty liver disease, certain cancers, T2DM, hypertension and dementia. Proposed mechanisms by which ITLC may confer health benefits include targeting inflammation, stress response, malnutrition, impaired metabolism, DNA damage, and microbial dysbiosis (Bodai, et al., 2018). In general, ITLC programs address all Six Pillars of lifestyle medicine as defined by the American College of Lifestyle Medicine with the aim of simultaneously impacting a range of disease drivers. These Six Pillars include physical activity, nutrition, sleep, social relationships, stress management, and avoidance of risky substances (American College of Lifestyle Medicine, 2020). Although ITLC overlaps significantly with the standard approach to diabetes management (e.g. DSMES emphasizing dietary improvement and increased exercise), ITLC is comparatively more comprehensive and more transformative.

A major factor limiting widespread adoption of ITLC is the investment of time and money required by many ITLC programs. Early ITLC programs required a residential experience, making large-scale implementation for community dwelling adults impractical. The Complete Health Improvement Program (CHIP) is a version of ITLC which was developed and validated for the ambulatory setting. CHIP is generally administered through a series of classes over a 1- to

3-month period. CHIP has been shown in an RCT to improve key biometrics and biomarkers relevant to type 2 diabetes, including glucose, systolic blood pressure, and LDL-C (Aldana et al. 2005, 371-381). This RCT included healthy adults and individuals with pre-existing diagnoses, such as hyperlipidemia, T2DM, and obesity. CHIP has been validated in multiple settings in the United States and internationally and has demonstrated sustained biomarker/biometric improvements at 36 months (Morton, et al., 2014; Kent, et al., 2013; Kotekal, et al., 2019). Of particular interest, when offered to Vanderbilt University and Vanderbilt Health System employees in a pilot scale study, CHIP was shown to improve key biomarkers and biometrics, to decrease diabetes medication use, and to decrease total cost of care on participants' employer-sponsored health plans by >\$1,000 per participant within 6-months (Shurney, et al., 2013). Another pilot study of individuals covered by Ohio University health insurance demonstrated improvement in biomarkers (Remy et al. 2017, 293-300) in an employed Appalachian population. The authors of the Ohio University study currently have a trial in progress assessing the effectiveness of CHIP for clinical outcomes, cost of care on the university health plan, and absenteeism which has enrolled university employees with various components of metabolic syndrome, including diabetes, prediabetes, obesity, overweight, hypertension, prehypertension, cardiovascular disease and dyslipidemia. Their study will compare outcomes including healthcare costs in the interventional group to those of an observational control group (Drozek 2020).

Despite promising evidence on the effectiveness of CHIP to achieve key outcomes, further study is needed to determine whether CHIP would be a viable population health tool from the perspective of a health insurance plan. It is important to note that many studies demonstrating various benefits of CHIP were conducted by potentially biased study teams linked to the Lifestyle Medicine Institute, which licenses CHIP (Aldana et al. 2005, 371-381; Kent et al.). In addition, aside from the Rockford, Illinois CHIP RCT publications (Merrill, Taylor, and Aldana 2008, 314-321; Aldana et al. 2005, 371-381), most CHIP studies have utilized pre-post designs without randomized control groups (Leibold et al. 2016, 84-91) and/or samples which may have been biased due to recruitment methodology (Kent et al. 2015; Shurney et al 2013; Drozek 2020). An RCT by a research team unaffiliated with the Lifestyle Medicine Institute is needed to confirm the generalizability of the clinical effectiveness of CHIP and to assess CHIP's ROI. Despite favorable pilot studies, to our knowledge there has never been a rigorous evaluation of a

population scale implementation of CHIP intended to improve the overall health and total cost of care of high-risk individuals such as patients with T2DM. Specifically, both the Vanderbilt and Ohio University studies addressing ROI are pilot scale and appear to lack rigorous randomized control groups, thus making them subject to selection bias. Both of these studies rely upon combinations of pre-post comparisons and comparisons between presumably motivated intervention groups that were actively enrolled in CHIP versus non-randomized, observational health plan member controls, which likely represents a less motivated population (Remy et al. 2017, 293-300; Anonymous; Drozek 2020). The lack of true randomization casts doubt upon the scale of ROI reported by Vanderbilt and ROI which may ultimately be reported by Ohio University. Unfortunately, implementing CHIP requires various licensing fees and per participant charges paid to the Lifestyle Medicine Institute, in addition to the local costs of administering the program. Even at large scale, CHIP can be expected to cost at least \$300-\$500 per participant. Due to this significant cost, it is imperative to rigorously evaluate the clinical and financial ROI of CHIP before implementing it at a population scale. Finally, to our knowledge there has never been a flexible online/in person application of CHIP. This could be an effective tool to bring CHIP to rural populations and might prove of general use in this era of uncertainty related to pandemics, climate events and other disruptions.

In the current study, we will implement a pilot-scale randomized controlled trial assessing the effectiveness of an adaptation of CHIP which utilizes a flexible hybrid online/in-person protocol. We hope to assess whether this protocol, offered to Geisinger Health Plan (GHP) members, enables CHIP to be administered effectively to a rural population while respecting current social distancing limitations necessitated by the pandemic. This pilot study at the Lewisburg YMCA at the Miller Center, a comprehensive health and wellness center owned jointly by Geisinger and Evangelical Community Hospital and administered by the YMCA. Through this pilot study, we hope to gain insight into whether and how such an application of CHIP could be a cost-effective tool for health plans such as GHP to achieve clinical and financial goals for adult members with T2DM. Through this pilot study, we hope to gain experience implementing CHIP at the Miller Center and to gain preliminary data to support efforts to obtain external funding in order to complete a full-scale clinical trial.

The Miller Center for Recreation and Wellness is a 501(c)3 not-for profit entity owned by a joint venture of Evangelical Community Hospital (ECH) and Geisinger. ECH possesses 51% interest in the joint venture, with Geisinger possessing 49%. As the slight majority member, ECH is responsible for day-to-day operations and operational/administrative oversight of the Center. The Miller Center does not have employees, rather, the Center is staffed with ECH and YMCA employees, and various other contractors for specific programs and services. ECH employees at the Miller Center are responsible for administrative oversight, accounting, facilities and maintenance, supply procurement, new business development, marketing and communications, and oversight of the Greater Susquehanna Valley YMCA operations to ensure that they are fulfilling their Management Services Agreement (MSA) with the Miller Center. The YMCA at the Miller Center is responsible for oversight of membership, the fitness center, sports and recreation, and childcare operations. The Miller Center is ultimately governed by a Board of Directors that is comprised of appointed representatives from ECH, Geisinger, the Greater Susquehanna Valley YMCA, and the community. The Miller Center is a Collaborating Institution under Evangelical Hospital's Federalwide Assurance.

4 HYPOTHESIS AND SPECIFIC AIMS

4.1 Hypothesis

Geisinger Health Plan members with T2DM offered CHIP in addition to standard insurance coverage will have improvement in HbA1c and improvements in other biometrics, biomarkers, psychometrics and utilization/financial outcomes, including LDL-C, systolic blood pressure, body mass index, waist circumference, number of diabetes medications prescribed, Wellbeing360 survey, and total cost of healthcare.

4.2 Specific Aim 1

To compare change in HbA1c, LDL-C, systolic blood pressure, body mass index, and waist circumference for GHP members offered CHIP versus members offered standard insurance coverage at 3- and 6-months.

4.3 Specific Aim 2

To compare number of diabetes drugs prescribed and total health care costs of GHP members offered CHIP versus GHP members offered standard insurance coverage at 3- and 6-months.

4.4 Specific Aim 3

To compare change in responses on the Wellbeing360 survey of GHP member offered CHIP versus employees offered standard employee wellness options

5 STUDY DESIGN

5.1 Description

This is a pilot randomized-controlled trial comparing the clinical, utilization, and financial outcomes of adult health plan members with T2DM offered CHIP versus those only offered standard health plan coverage.

5.2 Study Population

5.2.1 Approximate Number of Subjects

Approximately 60 adults who are Geisinger Health Plan members with Type 2 Diabetes Mellitus will participate in this study.

5.2.2 Inclusion Criteria

1. Geisinger Health Plan member for a full year prior to enrollment in the study, with plans to remain covered for a full year after the first study visit
2. HbA1c resulted within a year of enrollment in the study
3. ≥ 18 years
4. Current type 2 diabetes diagnosis
5. Living in the five-county region served by the Miller Center (Lycoming, Montour, Northumberland, Snyder and Union) with the ability to arrange their own transportation to the Miller Center in Lewisburg at least 10 times in a 3-month period
6. Access to computer, phone, or tablet with sufficient internet to complete program activities.

5.2.3 Exclusion Criteria

1. Presence of medical condition requiring specific diet other than gluten-free diet, a weight loss diet or diet directed at cardiovascular disease and/or metabolic syndrome (e.g. phenylketonuria)
2. Presence of medical condition contraindicating participation in CHIP, as determined by the Principal Investigator
 - a. Cancer on active treatment
 - b. Very advanced organ failure meeting one or more of the following criteria:
 - i. Heart
 1. On milrinone or dobutamine drip
 2. Presence of ventricular assist device (VAD)
 3. Listed for or received a heart transplant
 - ii. Lungs
 1. On home oxygen for COPD, interstitial lung disease, or any lung disease besides sleep apnea
 2. Listed for or received a lung transplant
 - iii. Liver
 1. Cirrhosis with MELD score ≥ 9
 2. Listed for or received a liver transplant
 - iv. Kidney
 1. On dialysis
 2. eGRF <15
 3. Listed for or received a kidney transplant
 - v. Dementia
 - vi. Severe difficulty swallowing
 - vii. Presence of any form of feeding tube
 - viii. Eating disorders (e.g. anorexia nervosa or bulimia)
 - ix. Malabsorption (does not include mild malabsorption such as in celiac disease)
 - x. Underweight status (BMI $< 18.5 \text{ kg/m}^2$)
 - xi. Stem cell transplant recipient

3. Diabetes in remission or already very tightly controlled with lifestyle alone, defined as HbA1c less than 6.5% on two separate occasions separated by at least 3 months while not on any diabetes medications. These must include the two most recent HbA1c values (i.e. if either of the last two HbA1c values was 6.5% or greater, the patient has had only one HbA1c value, *or* the patient was on a diabetes medication at the time of the HbA1c test, the patient is not excluded)
4. Pregnancy or plan to become pregnant within one year
5. Inability to give informed consent due to mental or psychiatric impairment
6. Any advanced neurological condition that would prevent a patient from altering their diet and/or participating in daily exercise?
7. Participation in the Fresh Food Farmacy program
8. Bariatric surgery within the past 2 years
9. Patient on warfarin
10. Hospice status
11. Cannot read and speak English fluently
12. Patient is currently enrolled in another clinical trial or plans to be within the next 12 months
13. Patient is not motivated (<7 out of 10) to improve their health through intensive lifestyle change
14. Patient has participated in intensive therapeutic lifestyle change through one of the following programs within the past 5 years:
 - a. Previous CHIP program
 - b. Ornish program
 - c. Pritikin program.

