5.7 Primary Endpoints

Clinical endpoint: Change in HbA1c at 6 months compared to baseline.

Feasibility endpoint: What proportion of individuals contacted agree to participate; what proportion of participants complete the intervention; what proportion of individuals contacted are excluded from the study based on lack of access to transportation or internet.

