5.9.1 Statistical Analysis Plan

Randomization scheme: The randomization scheme will be stratified on the potential study participant's most recent HbA1c value (< 6.5% vs \geq 6.5%).

Analysis methods: Descriptive statistics and plots for each variable will be inspected to identify influential points and to assess normality. Non-normally distributed variables will be transformed (e.g., logarithmic) as appropriate for parametric analysis, otherwise non-parametric methods will be used. Means, standard deviations, medians, ranges (maximum/interquartile) and 95%

confidence levels will be calculated for baseline outcome variables (HbA1c, LDL-C, systolic blood pressure) for the entire group, and stratified by CHIP vs. control group. The difference in outcomes will be calculated and treated as dependent variables. Since this is a pilot study the focus of the analysis will be estimating the mean and standard deviation of the change at 3- and 6-month for each primary and secondary outcome. We will also estimate the difference of the changes between groups and the variability. These estimates will then be used to design a larger scale study that will seek external funding. All estimates will be calculated under the ‘intent-to-treat’ principle. We will also collect and report on the proportion of individuals contacted and consent to participate, and compliance on attending the CHIP session. For those individuals contacted and do not agree to participate, we will collect the reason (e.g., not interested, lack of access to transportation, lack of internet, not able to reach).

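### Randomisation is stratified at HbA1c 6.5%, but section 5.9.1 does not use that stratum when estimating the HbA1c change that will inform the larger trial

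*Combined protocol and SAP*

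**What the plan says.** **Entry.** Section 5.2.2 sets no lower HbA1c limit. It asks only for "HbA1c resulted within a year of enrollment in the study". Criterion 3 in 5.2.3 excludes "Diabetes in remission or already very tightly controlled with lifestyle alone, defined as HbA1c less than 6.5% on two separate occasions", where the two values lie at least 3 months apart and were both obtained off all diabetes drugs. The same criterion says that if "the patient was on a diabetes medication at the time of the HbA1c test, the patient is not excluded". A person with only one HbA1c value on record, or with either of the last two values at 6.5% or above, also stays eligible.

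**Randomisation.** Section 5.9.1 stratifies on the "most recent HbA1c value (< 6.5% vs" 6.5% or above). Admitting people below 6.5% is therefore intended.

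**Endpoint and estimates.** The primary clinical endpoint (5.7) is "Change in HbA1c at 6 months compared to baseline". For change, 5.9.1 plans the mean and SD at 3 and 6 months and the between-group difference with its variability. It names neither the randomisation stratum nor baseline HbA1c in these estimates. The sentence about the whole group and the two arms concerns baseline variables. The sentences about change are general and do not rule out a table by stratum.

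**Use.** Section 5.9.1 adds: "These estimates will then be used to design a larger scale study that will seek external funding". The larger study's eligibility is not described. The hypothesis in 4.1 speaks of plan members with type 2 diabetes generally.

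**The concern.** The plan treats 6.5% as important enough to stratify randomisation on, then leaves it out of the estimates that are the pilot's main product. HbA1c change could plausibly behave differently on the two sides of the cut. People already below 6.5% have less room to fall. Section 8.2 also advises participants to ask their own providers whether medication changes are indicated. If drugs are reduced, a real benefit can show as a flat HbA1c. That advice covers every medicated participant and does not say that changes will happen, so this is a possibility rather than a plan.

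At stake is what the pilot can tell the designers of the next trial. A figure pooled over the strata answers the question for the same mix of participants. It does not show whether effect or spread differs by stratum, or which SD to use if the entry criterion were different. In addition, if the stratum predicts change, a between-arm difference estimated without it gives up some precision.

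**Working it through.** **1. The plan's own precision figures.** Inputs from 5.9.2: 30 per arm, 95% confidence, half-widths of 0.37 and 0.52 SD of the change.

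- Mean change: t(0.975, 29)/√30 = 2.045/5.477 = 0.373.
- Difference: t(0.975, 58) × √(2/30) = 2.002 × 0.2582 = 0.517.

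Both reproduce. They apply to all 30 per arm, with the strata combined.

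**2. Precision within strata.** The share p below 6.5% is not in the documents, so 20% to 40% is assumed, equal in both arms. The formulas are the same with the stratum's own n, and half-widths are in units of that stratum's SD.

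| p | n per arm, ≥6.5% | mean change | difference | n per arm, <6.5% | difference |
|---|---|---|---|---|---|
| 20% | 24 | 0.42 | 0.58 | 6 | 1.29 |
| 30% | 21 | 0.46 | 0.62 | 9 | 1.00 |
| 40% | 18 | 0.50 | 0.68 | 12 | 0.85 |

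Example: with 6 per arm, t(0.975, 10) × √(2/6) = 2.228 × 0.577 = 1.29.

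**3. How far pooled inputs could differ from those of the upper stratum.** Section 5.9.2 cites almost 300 per group from published data but gives no outcome, effect, SD, alpha or power, so it cannot be reproduced. It serves here only as an anchor. Assuming two-sided 5% and 80% power, 300 per group implies a standardised effect of (1.960 + 0.842) × √(2/300) = 0.229.

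Suppose this holds at ≥6.5%, with SD 1. Below 6.5%, let the effect be f × 0.229 and the SD be r. Let mean change in controls be the same in both strata. Then:

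- pooled difference = 0.229 × [(1−p) + p·f]
- control variance = (1−p) + p·r²
- CHIP variance = control variance + p(1−p) × [(1−f) × 0.229]²
- N per group = 2 × (1.960 + 0.842)² × (average variance)/(difference)² = 15.70 × (average variance)/(difference)²

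Example, p = 30%, f = 0, r = 0.5: difference 0.7 × 0.229 = 0.1603; control variance 0.7 + 0.3 × 0.25 = 0.775; CHIP variance 0.775 + 0.21 × 0.0524 = 0.786; average 0.7805; N = 15.70 × 0.7805/0.0257 = 477.

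| p | no effect, equal SD | no effect, half SD | half effect, half SD | same effect, half SD |
|---|---|---|---|---|
| 20% | 470 | 400 | 315 | 255 |
| 30% | 615 | 477 | 322 | 232 |
| 40% | 837 | 588 | 329 | 210 |

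With the same effect and the same SD in both strata, N stays at 300. Pooling can therefore raise N, lower it or leave it unchanged, depending on quantities that the documents do not give.

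**The case against.** The strongest reply is that nothing is wrong with the pooled figures. No section gives the larger trial an HbA1c floor. The stated interest is plan members with type 2 diabetes generally (section 3 and 4.1), and a trial with the same criteria and a similar mix should be planned from pooled inputs. This stands. A reader might infer that the pooled mean and SD misdescribe the population that the larger trial will target. The documents do not support that, because it presupposes an entry floor that they never mention.

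A reader might also infer that the next trial would be oversized by a definite factor. That follows only if the effect below 6.5% is assumed to be nil or small. The last column of the second table shows the opposite direction.

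Nor is the admission of these people an oversight. Criterion 3 keeps them in explicitly, stratification is meant to balance them between arms, and they can contribute to the other endpoints in 5.8, including medication count, cost, LDL-C, weight and blood pressure.

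Finally, strata of 6 to 12 per arm are weak evidence. With 6 in one arm, the 95% interval for an SD runs from about 0.6 to 2.5 times its estimate. The stratum also rests on the most recent value on file (5.4), which may be up to a year old (5.2.2), and not on the study's baseline measurement. Both limits stand and restrict how the stratum figures may be used. They do not explain why the analysis should omit a factor used in the randomisation.

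**Conclusion.** The point holds as an analysis gap, not as a fault in eligibility. The trial knowingly admits people below 6.5% and randomises within strata at that value, but 5.9.1 does not use the stratum for HbA1c change or for the between-arm difference. Pooled estimates are valid for a larger trial with the same criteria and a similar mix. They cannot show whether effect or SD differs by stratum, or what SD would apply under a different HbA1c entry criterion.

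The size and direction of any difference are unknown. The range of 210 to 837 per group around 300 illustrates that uncertainty and is not an estimate. It rests on assumed shares of 20% to 40%, assumed effects and SDs below 6.5%, and assumed 80% power at two-sided 5%.

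**What to change.** In 5.9.1:

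- Keep the overall mean and SD of change and the overall between-arm difference.
- Estimate the between-arm difference in HbA1c change with the randomisation stratum in the analysis.
- Add a descriptive table, for each stratum (<6.5% and ≥6.5%), with n, the mean and SD of HbA1c change by arm, and the between-arm difference with its 95% CI. Show the change in number of diabetes medications beside it.
- State that these figures will inform, but not alone determine, the planning SD and the population of the larger trial.

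The cost is one extra table from data already collected, with no added visits or measurements. The downside is wide intervals below 6.5%: the half-width of the difference is about 1.29 SD with 6 per arm, and still 0.85 SD with 12. The table should be labelled descriptive. The pilot's eligibility criteria need not change.
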